### **Primary outcome analysis**

The primary outcome is externalising difficulties measured using the conduct problems and hyperactivity subscales of the Strengths and Difficulties Questionnaire (Goodman et al., 1998). It will be included in the model as one total score (Goodman et al., 2010).

The model will have three levels, nesting pupil within school, and school within LA/CA. These will be fixed effects due to this being an efficacy trial, as well as the small number (minimum 2) of schools within each LA/CA. Given the small number of schools nested within each LA/CA, this top level of nesting may be adjusted or removed from the model.

For pupil (i) in school (j) in LA/CA (k), we define the model as:

$$\begin{aligned} (\text{Externalising difficulties}_{ijk}) = & \beta_0 + \beta_1(\text{group allocation}_{jk}) + \beta_2(\text{measurement time}_{jk}) + \beta_3(\text{group} \\ & \text{allocation}_{jk}) * (\text{measurement time}_{jk}) + \beta_4(\text{cohort}_{jk}) + \beta_5(\text{year group}_{ijk}) + \beta_6(\text{gender}_{ijk}) + u_{0jk} + v_{0k} \\ & + e_{ijk} \end{aligned}$$

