## Analysis

Analyses will be conducted by an analyst masked to intervention group assignment following the intention-to-treat principle. The hypotheses and general analysis framework were decided a priori; the analysis plan was written and finalised during the period of data collection after recruitment but before baseline data collection was completed. The analyses will use maximum likelihood estimation meaning all participants will be included, even those with missing follow up data points, in line with the intention-to-treat principle. There will be two approaches to handling missing data, assuming that data are missing at random: 1) multiple imputation of data at any time point using wide format data, and 2) participants who have at least one post-randomisation observation will be included in the model with maximum likelihood estimation. Results will be compared using the two approaches. The chosen analysis model to assess the intervention effect is a mixed effects model. This model will form the basis of the main trial report that will be submitted for publication. Fixed effects will include group allocation (intervention/control), time (mid-programme/end of programme), and the interaction between group allocation and time. Random intercepts for pupils or staff nested within schools will also be specified, depending on whether the outcome is pupil- or staff-specific. The baseline level of the outcome will be included as a covariate to increase power and precision. Cohort (1/2), year group (8/9) and gender (dummy coded: male/female/gender diverse, reference: male) will be included as fixed effect prognostic factors to improve precision of the treatment effect. LA/CA was used as a stratifier in the randomisation, and it is intended to be included in the analysis as a fixed effect. However, there may be issues with model estimation due to a small number of schools per LA/CA (minimum of two). In this case, we will specify a three-level model (pupil, school, LA) or remove LA/CA as a fixed effect from the analysis. For the mixed effects models, the package *lme4* version (version 1.1-35.1) in R will be used (Bates et al., 2015). Interaction terms will be specified within the mixed effects models. Example syntax for the primary outcome of pupil externalising symptoms with LA/CA included as a fixed effect is:

```

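### The SAP does not define one primary model: the Analysis text, the example syntax and the Primary outcome analysis equation differ on the baseline score, the pupil effect, the school effect and LA/CA

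*SAP*

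**What the plan says.** The SAP describes the primary model in three places.

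- **Analysis, text.** A mixed effects model with group, mid- and end-of-programme time, and their interaction. On clustering it says "Random intercepts for pupils or staff nested within schools will also be specified", and on the starting score it says "The baseline level of the outcome will be included as a covariate to increase power and precision". Cohort, year group and gender (three categories, dummy coded with male as reference) are added. LA/CA, the randomisation stratifier, is meant to enter as a fixed effect. If estimation proves difficult, "we will specify a three-level model (pupil, school, LA) or remove LA/CA as a fixed effect from the analysis".
- **Analysis, example syntax for the primary outcome.** It contains the baseline score, two gender terms and LA/CA as a fixed term. The random part is `(1 + school | pupil)`.
- **Primary outcome analysis.** It sets out a structure with pupils, schools and LA/CA as its levels and says of them "These will be fixed effects due to this being an efficacy trial". As a second reason it points to how few schools an LA/CA may hold, the minimum being two. It goes on to allow that "this top level of nesting may be adjusted or removed from the model". An equation follows, introduced by "For pupil (i) in school (j) in LA/CA (k), we define the model as". Its terms are group, time, group by time, cohort, year group, a single gender coefficient, `u_0jk`, `v_0k` and `e_ijk`.

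Secondary outcome analysis applies the primary specification to the other pupil outcomes and, with staff in place of pupils, to the staff outcomes. Presentation of outcomes takes the adjusted mean difference at each time point as the numerator of the effect size.

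**The concern.** An analyst could follow any of the three descriptions and claim to have followed the plan, yet they are different models. The equation is the formal definition, and it lacks the baseline score that the Analysis section requires. It also has nothing to link the two follow-up scores of the same pupil. The sentence on fixed effects conflicts with the random intercepts in the Analysis section and with the equation's own `u_0jk` and `v_0k`.

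The precision of the primary estimate, the standard error of the group-by-time term and, on one reading of the fixed-effects sentence, the existence of the estimate all depend on which description is used. The ambiguity carries over to every secondary model that inherits the specification.

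**Working it through.** **1. The three descriptions side by side**

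| Element | Analysis, text | Example syntax | Primary outcome analysis |
|---|---|---|---|
| Baseline score | covariate | included | absent from equation |
| Pupil | random intercept | random intercept plus school slopes by pupil | no term |
| School | random intercept | no intercept shared by a school's pupils | `u_0jk`, but text can be read as fixed |
| Occasion | two follow-ups | time term | outcome and residual indexed `ijk` only |
| Gender | two dummies | two terms | one coefficient |
| LA/CA | fixed; fallback is a third level or removal | fixed | level with `v_0k`, called fixed, may be adjusted or removed |

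In lme4, `(1 + school | pupil)` lets the effect of school vary by pupil. It does not nest pupils in schools, so the syntax cannot settle the conflict.

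**2. Can the group effect be estimated?** Inputs: 62 schools, 31 per arm, allocation constant within school, two follow-up times with mid-programme as reference. The columns are intercept, group, time and group by time (4), plus any dummies. The number of LA/CA strata is not given; 15 is assumed, each holding both arms. The result for school does not depend on it.

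- LA/CA fixed only: 4 + 14 = 18 columns, rank 18. All group effects can be estimated.
- School fixed: 4 + 61 = 65 columns, rank 64. The mid-programme difference (β1) and the end-of-programme difference (β1 + β3) cannot be estimated; β3 can.
- School and LA/CA fixed: 65 + 14 = 79 columns, rank 64. Same result.

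**3. The plan's own sample size figure.** Inputs from the sample size section: difference 5.21 − 4.7 = 0.51, SD 2.96, ICC 0.041, m = 219.73, CV 0.366, power 0.8, two-sided 0.05.

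- Pupils per arm without clustering: 2 × (2.96 × 2.8016 / 0.51)² = 528.8.
- Design effect: 1 + 218.73 × 0.041 = 9.968. Schools per arm: 528.8 × 9.968 / 219.73 = 23.99.
- Unequal clusters: L = 219.73 × 0.041 / 9.968 = 0.904, and 23.99 / (1 − 0.366² × 0.904 × 0.096) = 24.27.

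This matches the stated 24.3 schools. It also gives 5,333.03 pupils against the stated 5,333.02, and 24.27 / 0.85 = 28.6, so 29 schools. The figure is not in dispute. L shows that about 90% of the variance of a school mean lies between schools.

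**4. What baseline adjustment is worth.** With k = 31 schools per arm and equal cluster sizes,

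MDES = 2.8016 × √{(2/31) × [0.041(1 − r_s²) + 0.959(1 − r_p²)/219.73]},

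where r_s and r_p are the school- and pupil-level pre-post correlations. Both are assumptions; the SAP says that evidence on the correlation is lacking and did not use one.

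| r_p | r_s | MDES |
|---|---|---|
| 0 | 0 | 0.152 |
| 0.5 | 0 | 0.150 |
| 0.7 | 0 | 0.148 |
| 0.5 | 0.5 | 0.131 |
| 0.7 | 0.7 | 0.108 |

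**5. What the missing pupil intercept does.** Without it, the two scores of a pupil are treated as independent given school. For group by time, the pupil-level standard error is then overstated by 1/√(1 − ρ), where ρ is the within-pupil correlation: 1.41 at 0.5, 1.58 at 0.6 and 1.83 at 0.7 (assumed values). The difference at a single time point is much less affected, because between-school variance dominates it.

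**6. Room for LA/CA.** With at least two schools per stratum, 62 schools give at most 31 strata, leaving at least 62 − 31 − 1 = 30 between-school degrees of freedom. After 15% school attrition (62 × 0.85 ≈ 53 schools), the same worst case leaves about 53 − 31 − 1 = 21, and some strata would hold a single school.

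**The case against.** The strongest reply is that the intended model can be recovered. The Analysis section calls for a mixed model with random intercepts and the baseline score. The syntax includes that score, and Design overview lists a baseline for the primary outcome. Its absence from the equation therefore looks like an omission and not a decision to discard it. That is fair, but the equation is presented as the definition of the model, and the syntax that might overrule it is itself wrong in its random part.

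A reader might infer that the SAP makes school a fixed effect, so that the trial yields no treatment estimate. The document does not support that as the intended meaning. The pronoun is ambiguous, and one of its two reasons, the few schools per LA/CA, concerns only LA/CA. The equation carries `u_0jk`, the staff models are described as differing only in the random intercept, and ICCs are promised for all models. With LA/CA alone fixed, every group effect can be estimated.

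A reader might also infer that the two sections contradict each other on dropping the stratifier, or that it could be dropped once results are known. Neither holds. Both sections permit removal, the Analysis section ties it to estimation problems, and the analyst is masked to allocation. What stands is narrower: the Analysis section offers two fallbacks without saying which comes first, and the Primary outcome analysis section gives no criterion beyond small strata.

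**Conclusion.** The point holds as a failure to define one primary model. The equation omits the baseline score, the pupil intercept and the occasion index, and collapses gender to one coefficient. The fixed-effects sentence conflicts with the Analysis section and with the equation itself, and the syntax does not express pupils nested in schools.

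The cost of following the equation is uncertain. A large loss from omitting baseline should not be inferred from a pupil-level correlation alone: that moves the detectable effect only from 0.152 to 0.148 to 0.150. A fall to 0.131 to 0.108 requires a school-level correlation of 0.5 to 0.7 as well. The distortion of the group-by-time standard error likewise depends on an assumed within-pupil correlation. The inability to estimate the group differences is conditional on applying the sentence to school. The contradiction itself depends on none of these figures, and it must be corrected because it concerns the primary analysis.

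**What to change.** Replace the text and equation under Primary outcome analysis with one model:

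Y_tijk = group + time + group × time + baseline externalising + cohort + year group + two gender dummies + LA/CA fixed effects + random school intercept + random pupil-within-school intercept + e_tijk.

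Then:

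- Limit any wording on fixed effects to LA/CA.
- Change the random part of the syntax to `(1 | school/pupil)`, or to `(1 | school) + (1 | pupil)` with unique pupil identifiers.
- State one ordered fallback for LA/CA, the same in both sections and triggered by a defined estimation failure, with a random LA/CA intercept tried before any removal.

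The cost is SAP wording. Keeping LA/CA uses some between-school degrees of freedom, and fewer will be available if schools withdraw.

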### **Secondary outcome analysis**

Additional pupil outcomes will be included as part of the secondary outcome analysis. The same model specification will be used as for the primary outcome, and separate models will be specified for each of the outcomes. All outcomes are measured at baseline, mid-programme, and end of programme, unless otherwise specified.

- Internalising difficulties measured using the sum score of emotional symptoms and peer problems sub-scales of the Strengths and Difficulties Questionnaire (SDQ; Goodman et al., 1998)
- Impact of mental health difficulties measured using the impact score of the SDQ
- Prosocial behaviour measured using the prosocial behaviour subscale of the SDQ
- Teacher-student relationships measured using the teacher-student relationships subscale of the Student Engagement Instrument (SEI; Appleton et al., 2006)
- Peer support for learning measured using the peer support for learning subscale of the SEI
- Control and relevance of school work measured using the control and relevance of school work subscale of the SEI
- Future aspirations and goals measured using the future aspirations and goals subscale of the SEI
- Bullying perpetration measured using the bullying perpetration subscale of the Illinois Bully Scale (IBS; Espelage & Holt, 2001)
- Bullying victimisation measured using the bullying victimisation subscale of the IBS
- School attendance using local school data at mid-programme and end-of-programme
- School exclusions using local school data at mid-programme and end-of-programme
- Permanent school exclusions using local school data at mid-programme and end-of-programme
- Longer-term school attendance will be measured using data from the National Pupil Database after winter 2025
- Longer-term school exclusions will be measured using data from the National Pupil Database after winter 2025
- Longer-term permanent school exclusions will be measured using data from the National Pupil Database after winter 2025
- Academic attainment will be measured using Key Stage 4 attainment after winter 2025.

Staff secondary outcome analysis will follow the same specification as the primary outcome analysis, except that the random intercept will be staff nested within schools. All outcomes are measured at baseline, mid-programme, and end of programme, unless otherwise specified.

The following outcomes will be considered in separate models:

- Underlying causes of problem behaviour and symptoms measured using the underlying causes of problem behaviour and symptoms subscale of the Attitudes Related to Trauma-Informed Care (ARTIC 35; Baker et al., 2021)
- Self-efficacy at work measured using the self-efficacy at work subscale of the ARTIC 35
- Response to problem behaviour measured using the response to problem behaviour subscale of the ARTIC 35
- Reactions to work measured using the reactions to work subscale of the ARTIC 35
- Empathy and control measured using the empathy and control subscale of the ARTIC 35
- Compassion satisfaction measured using the compassion satisfaction subscale of the Professional Quality of Life Scale (ProQOL; Stamm 2010)
- Compassion fatigue measured using the compassion fatigue subscale of the ProQOL

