		
response to problem behaviour, 4) reactions to work, 5) empathy and control
 
Measure B: Professional Quality of Life Scale (ProQOL) (Stamm, 2010)
 
Outcomes: wellbeing, burnout
 
Variables: 6) compassion satisfaction, 7) compassion fatigue, 8) burnout
 
Local school data
 
Outcome: academic attendance and exclusions
 
Variables: 1) attendance, 2) fixed-term exclusions, 3) permanent exclusions

Baseline for primary outcome	variable	Externalising difficulties
	measure (instrument, scale, source)	Conduct problems and hyperactivity subscales of the Strengths and Difficulties Questionnaire (Goodman et al., 1998)
Baseline for secondary outcome	variable	
Pupil-reported surveys
 
Variables: 1) internalising difficulties, 2) no baseline for impact score, 3) prosocial behaviour
 
Variables: 4) teacher-student relationships, 5) peer support for learning, 6) control and relevance of school work, 7) future aspirations and goals
 
Variable: 8) bullying perpetration, 9) bullying victimisation
 
Staff-reported surveys
 
Variables: 1) underlying causes of problem behaviour and symptoms, 2) self-efficacy at work, 3) response to problem behaviour, 4) reactions to work, 5) empathy and control

		
Variables: 6) compassion satisfaction, 7) compassion fatigue, 8) burnout
 
Local school data
 
Variables: 1) attendance, 2) fixed-term exclusions, 3) no baseline for permanent exclusions (given their relatively low frequency)

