lmer(externalising ~ group * time + (1 + school | pupil) + baseline_externalising + cohort_1_2 + year_group_8_9 + male_female + male_diverse + LA_CA, data = MGDAS_data)
```

Subgroup analyses and further analyses are detailed in the relevant sections below.

Standard data quality checks will be performed in the data preparation stage before analysis, including impossible values, distribution of scores and residuals, outliers, low frequency categorical variables, linearity, and homogeneity of variance. Violations will be managed with

appropriate techniques. Descriptive statistics of the implementation data will be used to identify levels of implementation and engagement.

There are no planned interim analyses for efficacy.

This project contains multiple secondary outcomes and analyses. For pupils, there are 16 secondary outcomes, and, for staff, there are 7 secondary outcomes. As a result, there is a higher risk of false positives overall. To mitigate this, false discovery rate (FDR) multiple comparison correction will be applied to the significance level for tests for outcomes that are within the same measure, as these are likely to be correlated both theoretically and statistically. For example, FDR correction will be applied to three SDQ secondary pupil outcomes. In a similar vein, FDR correction will be applied to subgroup and further analyses. Some of these analyses will be underpowered, increasing the chance of false negatives in some cases. All exploratory analyses must therefore be treated with caution and not interpreted individually.

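### One linear repeated-measures model and a standardised mean difference are prescribed for all 16 pupil secondary outcomes, but do not suit exclusions, the longer-term outcomes or the two outcomes without a baseline

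*SAP*

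**What the plan says.** The Secondary outcome analysis section sets one rule for pupil outcomes: "The same model specification will be used as for the primary outcome, and separate models will be specified for each of the outcomes". It then lists the outcomes without exempting any from the model. The Analysis section counts them: "For pupils, there are 16 secondary outcomes, and, for staff, there are 7 secondary outcomes".

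The specification being carried over is set out in the Analysis section:

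- Software: "For the mixed effects models, the package *lme4* version (version 1.1-35.1) in R will be used". The example call begins "lmer(externalising ~ group * time + (1 + school | pupil) + baseline_externalising + cohort_1_2", which is a linear mixed model with a pupil-level random term and the baseline score.
- Time structure: "Fixed effects will include group allocation (intervention/control), time (mid-programme/end of programme), and the interaction between group allocation and time".
- Effect measure: the only one named under Presentation of outcomes is an SMD, scaled by the pooled unconditional variance.

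The list includes these entries:

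- "Permanent school exclusions using local school data at mid-programme and end-of-programme". For this outcome the Design overview table records "no baseline for permanent exclusions (given their relatively low frequency". The same table records no baseline for the SDQ impact score.
- "Academic attainment will be measured using Key Stage 4 attainment after winter 2025". Longer-term attendance, exclusions and permanent exclusions from the National Pupil Database are given the same timing.

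The equation under Primary outcome analysis keeps time and group-by-time but has neither a baseline term nor a pupil random effect.

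**The concern.** A blanket rule works only if every outcome has the primary outcome's shape: a roughly continuous score, taken at baseline and at both follow-up visits. Several listed outcomes do not.

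- **Outcome type.** Permanent exclusion is an infrequent event. A mean difference divided by a standard deviation gives a school or policy reader neither a risk nor a ratio.
- **Time points.** Four outcomes arise after the programme, so a mid/end factor has no meaning for them.
- **Baseline.** Two outcomes have no baseline, while the Analysis section makes the baseline score part of the model.

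All of this is known now. If the rule stays, the analyst must either report hard-to-read effects or choose a different model once the data are in hand, which is the freedom that a SAP is meant to remove.

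**Working it through.** **1. Count the outcomes.** The pupil list has 9 survey outcomes, 3 from local school data and 4 longer-term: 9 + 3 + 4 = 16. This matches the SAP's figure.

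**2. Compare each outcome with the specification.**

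| Outcome | Own baseline (Design overview) | Mid and end visits | Mismatch |
|---|---|---|---|
| SDQ impact score | No | Yes | Baseline term |
| Permanent exclusions (local) | No | Yes | Baseline term; rare event |
| Fixed-term exclusions (local) | Yes | Yes | Outcome type (weaker) |
| Longer-term attendance | Not stated | No | Time terms |
| Longer-term exclusions | Not stated | No | Time terms; outcome type |
| Longer-term permanent exclusions | Not stated | No | Time terms; rare event |
| Key Stage 4 attainment | Not stated | No | Time terms |

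That is 7 of 16. The other nine (eight survey scales and local attendance) have a baseline and both visits. The Secondary outcome analysis list mentions only mid- and end-of-programme data for local attendance and exclusions; the Design overview gives attendance and fixed-term exclusions a baseline, and I have followed the latter.

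**3. Can the time terms be estimated?** The fixed part is [1, group, time, group × time], four columns. With two visits its rank is 4. With one record per pupil, time is constant: its column repeats the intercept and group × time repeats group, so the rank is 2. Time and group × time then cannot be estimated, and a pupil intercept cannot be separated from the residual. One record per pupil is an assumption. It is the ordinary case for Key Stage 4; the SAP does not say how many National Pupil Database records will be used.

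**4. What an SMD does to a rare event.** The SAP gives no exclusion rates, so take control-arm risks of p = 0.1% and 0.5% as assumptions, halved in the intervention arm, with the baseline arm sizes 6,429 (intervention) and 7,194 (control) all followed.

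- Expected events: 6,429 × p/2 + 7,194 × p = 3.2 + 7.2 ≈ 10 at 0.1%, and 16.1 + 36.0 ≈ 52 at 0.5%.
- Pooled variance: [6,429 × (p/2)(1 − p/2) + 7,194 × p(1 − p)] / 13,623 = 0.000763 at 0.1% and 0.003804 at 0.5%. The square roots are 0.0276 and 0.0617.
- SMD = (p/2) / pooled SD: 0.0005 / 0.0276 = 0.018, and 0.0025 / 0.0617 = 0.041.

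The risk ratio is 0.5 in both cases. The SMD more than doubles only because the assumed base rate changes.

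**5. Does the linear form lose power?** Ignoring clustering, with √(1/6,429 + 1/7,194) = 0.01716:

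- Linear difference: z = SMD / 0.01716 = 1.05 at 0.1% and 2.36 at 0.5% (from unrounded SMDs).
- Log risk ratio: z = ln 2 / √(1/e₁ − 1/n₁ + 1/e₂ − 1/n₂), with e the events and n the pupils per arm: 0.693 / 0.671 = 1.03 and 0.693 / 0.300 = 2.31.

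Detection is essentially the same. The pooled standard error is about 1.9% larger than the one allowing unequal variances, a trivial difference.

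**6. Baseline term.** The Analysis text and example call include the baseline score; the primary-outcome equation does not. The impact score and permanent exclusions can be fitted under the equation, but not under the text and call unless the covariate is dropped.

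**The case against.** The best defence is that the SAP under-specifies rather than prescribes wrongly. The lmer call is offered as an example for the primary outcome, lme4 also fits generalised models, and the plan promises to check score distributions, sparse categories and variance homogeneity and to deal with violations. That promise names no model, link, trigger or effect measure, and it cannot supply visits or baselines that are absent. The rule itself is explicit.

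Three parts of the defence do stand, and each blocks a stronger reading that a reader might infer.

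- **That six outcomes (four longer-term, two without baseline) cannot be fitted at all.** The documents do not support this. The two without a baseline can be fitted under the primary-outcome equation or by omitting the covariate. For the National Pupil Database outcomes the number of records per pupil is not stated, and the section on longitudinal follow-up places those three analyses after the funded study, as uncosted work.
- **That the linear model costs power for exclusions.** At the assumed rates it does not: rarity limits detection under either form. With large clusters a linear model can also be defended as estimating a risk difference, though the SAP reports an SMD instead.
- **That an SMD of 0.018 to 0.041 should be judged against the 0.17 MDES.** That MDES was calculated for externalising difficulties with its own SD and intracluster correlation. It is no benchmark for exclusions.

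The SAP also does not define fixed-term exclusions as counts, days or yes/no, so the concern about outcome type is firmest for permanent exclusions.

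**Conclusion.** The concern holds as a fault of specification and effect measure in the secondary analyses. Seven of the 16 pupil outcomes are poorly served by the common rule in at least one respect.

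- Permanent exclusions: the SMD is hard to interpret. The 0.018 to 0.041 for a halved risk rests on assumed rates of 0.1% to 0.5%; the low frequency itself is the SAP's own statement. Fixed-term exclusions share the problem to a lesser degree.
- Key Stage 4 attainment and the National Pupil Database outcomes: the mid/end terms do not apply, and with one record per pupil they and the pupil intercept cannot be estimated. The matter is less pressing for the three database outcomes because of their timing.
- Impact score and permanent exclusions: the Analysis text, the example call and the primary-outcome equation must be reconciled on the baseline term.

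The primary outcome is not affected, and no loss of power is shown.

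**What to change.** Replace the blanket sentence in the Secondary outcome analysis section with a table giving, for each outcome, its type, time points, baseline term, model and effect measure. For the affected outcomes:

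- **Permanent exclusions:** one cumulative yes/no per pupil in a logistic model clustered by school (mixed or GEE), without a baseline term, reported as an odds or risk ratio with the risk difference. If events are too few, by a number fixed in advance, report counts by arm with a school-level permutation test that permutes within the LA/CA strata used for randomisation.
- **Fixed-term exclusions:** state how the variable is recorded. If it is a count, use a count model clustered by school, such as negative binomial, with the baseline count, reported as a rate ratio. Include an offset for possible sessions or observation time only if that is collected; the SAP does not say that it is.
- **Key Stage 4 and National Pupil Database outcomes:** a single-time-point model with a school random effect and no time, group-by-time or pupil intercept, of a type that suits the outcome. If several database periods are to be used, define them.
- **SDQ impact score:** omit the own-baseline term, or adjust for baseline SDQ internalising and externalising scores, which are collected.

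Also bring the Analysis text, the example call and the primary-outcome equation into agreement on the baseline term.

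The cost is SAP wording and some extra modelling, with no new data collection. The main downside is possible non-convergence for rare events, which the stated fallback covers.
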